Medication number	A unique identifier on the label of medication kits
Patient	An individual with the condition of interest for the study
Screen Failure	A patient who did not meet one or more criteria that were required for participation in the study
Source Data/Document	Source data refers to the initial record, document, or primary location from where data comes. The data source can be a database, a dataset, a spreadsheet or even hard-coded data, such as paper or eSource.
Study treatment	Any single drug or combination of drugs or intervention administered to the patient as part of the required study procedures.
Study treatment discontinuation	When the patient permanently stops taking study drug prior to the defined study treatment completion date (if any) for any reason; may or may not also be the point/time of study discontinuation
Study treatment interruption	When the patient temporarily stops taking study drug
Subject	A trial participant (can be a healthy volunteer or a patient)
Patient number	A unique number assigned to each patient upon signing the informed consent. This number is the definitive, unique identifier for the patient and should be used to identify the patient throughout the study for all data collected, sample labels, etc.
Variable	A measured value or assessed response that is determined from specific assessments and used in data analysis to evaluate the drug being tested in the study
Withdrawal of study consent	Withdrawal of consent is defined as when a patient does not want to participate in the study any longer, and does not want any further visits or assessments, and does not want any further study related contact, and does not allow analysis of already collected biologic material.

Amendment 1 (06-Mar-2019)

Amendment rationale

The primary purposes of this protocol amendment are to:

- Update the pregnancy prevention language to align with the Clinical Trials Facilitation Group (CTFG) recommendations related to contraception and pregnancy testing in clinical trials.

■ [REDACTED]

- Add a follow-up period of 12 months for patients who have sustained remission at month 12 to obtain further data on response and remission duration.
- Add a new secondary objective related to the newly added 12 months follow-up period.
- Update the drug induced liver injury (DILI) guidance to align with current Novartis DILI guidelines.
- Update to align with the current eltrombopag program risk language.

Changes to the protocol:

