6.5.2 Dose modifications

For patients who do not tolerate the protocol-specified dosing schedule, dose interruptions and/or reductions are either recommended or mandated in order to allow patients to continue the study treatment.

These dose modifications are summarized in [Table 6-3](#). Deviations to mandatory dose interruptions and/or reductions are not allowed. Permanent treatment discontinuation is mandatory for specific events indicated as such in [Table 6-4](#).

Table 6-3 Eltrombopag Dose Adjustments in ITP

Platelet count	Dose adjustment or response
< $100 \times 10^9/L$ following 2 weeks of therapy	Increase daily dose by 25 mg to a maximum of 75 mg/day ^a
$\geq 100 \times 10^9/L$ to $< 200 \times 10^9/L$	Use lowest dose of eltrombopag to maintain platelet counts around $100 \times 10^9/L$ for 2 months prior to per protocol tapering ^a
$\geq 200 \times 10^9/L$ to $\leq 400 \times 10^9/L$	Decrease daily dose by 25 mg. Wait 2 weeks to assess the effects of this and any subsequent dose adjustments ^{b c}
$> 400 \times 10^9/L$	Stop eltrombopag; increase the frequency of platelet monitoring to twice weekly. Once the platelet count is $< 150 \times 10^9/L$, reinitiate therapy at a lower daily dose ^{b c}

a. This dose adjustment schedule was chosen for this study to have patients use the minimal efficacious dosage of eltrombopag in order to achieve a CR. Patients need to maintain a CR for a minimum of 2 months before tapering off can be attempted.

b. For patients taking eltrombopag once daily, consideration should be given to dosing at 12.5 mg once daily or alternatively a dose of 25 mg once every other day

c. Source: The latest version of the eltrombopag core data sheet (CDS).

These dose changes must be recorded on the appropriate CRF.

Eltrombopag can cause hepatobiliary laboratory abnormalities, severe hepatotoxicity, and potentially fatal liver injury. Serum ALT, AST and bilirubin should be measured prior to initiation of eltrombopag, every 2 weeks during the dose adjustment phase and monthly after establishment of a stable dose. Abnormal serum liver tests should be evaluated with repeat

testing within 3 to 5 days. If the abnormalities are confirmed, serum liver tests should be monitored weekly until the abnormalities resolve, stabilize, or return to baseline levels.

For the grading of adverse events and laboratory results, the Common Terminology Criteria for Adverse Events (CTCAE) Version 4.03 will be used.

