Table 6-4 Criteria for dose adjustment based on liver enzyme and bilirubin levels

Dose modifications for ETB115	
Worst toxicity CTCAE^a Grade (value) during the treatment	Investigations (Hepatic)
Isolated Total Bilirubin Elevation	
> ULN – 1.5 x ULN	Maintain dose level
> 1.5 - 3.0 x ULN*	Interrupt dosing and weekly monitor liver function tests (LFTs) ^b , or more frequently if clinically indicated, until resolved to $\leq 1.5 \times$ ULN: If resolved in ≤ 14 days, then resume at same dose level If resolved in > 14 days, then decrease one dose level ^e
> 3.0 - 10.0 x ULN**	Mandatory: Interrupt dosing and weekly monitor LFTs ^b , or more frequently if clinically indicated, until resolved to $\leq 1.5 \times$ ULN: If resolved in ≤ 14 days, then decrease one dose level ^e If resolved in > 14 days, then discontinue patient from study drug treatment. LFTs ^b will continue to be monitored weekly, or more frequently if clinically indicated, until total bilirubin have resolved to baseline or stabilization over 4 weeks.
> 10.0 x ULN	Mandatory: Discontinue patient from study drug treatment The patient should be monitored weekly (including LFTs ^b), or more frequently if clinically indicated, until total bilirubin have resolved to baseline or stabilization over 4 weeks.
	* Note: If total bilirubin $> 1.5 - \leq 3 \times$ ULN is due to the indirect (non-conjugated) component only, no changes to dose are required. ** Note: If total bilirubin $> 3.0 - 10.0 \times$ ULN is due to the indirect (non-conjugated) component only, and hemolysis as the etiology has been ruled out as per institutional guidelines (e.g., review of peripheral blood smear and haptoglobin determination), then decrease 1 dose level ^e and continue treatment at the discretion of the investigator
Isolated AST or ALT elevation	
> ULN - 3.0 x ULN	Maintain dose level
> 3.0 - 5.0 x ULN	Maintain dose level. Repeat LFTs ^b as soon as possible, preferably within 48-72 hours from awareness of the abnormal results. If abnormal lab values are confirmed upon the repeat test, then monitor LFTs ^b weekly, or more frequently if clinically indicated, until resolved to $\leq 3.0 \times$ ULN Discontinue patient from the study drug treatment if elevation is combined with any of the following: Clinical symptoms of liver injury or evidence for hepatic decompensation

Dose modifications for ETB115	
Worst toxicity CTCAE^a Grade (value) during the treatment	Investigations (Hepatic)

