	Progressively increasing LFTs ^b upon repeat testing Persistence ≥ 4 weeks
> 5.0 - 10.0 x ULN	Mandatory: Interrupt dose. Repeat LFTs ^b as soon as possible; preferably within 48-72 hours from awareness of the abnormal results. Monitor LFTs ^b weekly, or more frequently if clinically indicated until resolved to $\leq 3.0 \times$ ULN then: If resolved in ≤ 14 days, maintain dose level If resolved > 14 days, decrease one dose level ^e Mandatory: Interrupt dose. Repeat LFTs ^b as soon as possible, preferably within 48-72 hours from awareness of the abnormal results. Monitor LFTs ^b weekly, or more frequently if clinically indicated until resolved to \leq baseline. Then decrease one dose level ^e
> 10.0 - 20.0 x ULN	Mandatory: Discontinue patient from study drug treatment Repeat LFTs ^b as soon as possible, preferably within 48-72 hours from awareness of the abnormal results. Monitor LFTs ^b weekly, or more frequently if clinically indicated until resolved to \leq baseline or stabilization over 4 weeks..
Combined^c elevations of AST or ALT and total bilirubin	
For patients with normal baseline ALT and AST and total bilirubin value [AST or ALT $> 3.0 \times$ ULN] combined with [total bilirubin $> 2.0 \times$ ULN] without evidence of cholestasis ^d OR For patients with elevated baseline AST or ALT [AST or ALT $> 3 \times$ baseline] OR [AST or ALT $> 5.0 \times$ ULN], whichever is lower, combined with [total bilirubin $> 2 \times$ baseline AND $> 2.0 \times$ ULN]	Mandatory: Permanently discontinue patients from study drug treatment. Repeat as soon as possible, preferably within 48 hours from awareness of the abnormal results, then with weekly monitoring of LFTs ^b), or more frequently if clinically indicated, until AST, ALT, or bilirubin have resolved to baseline or stabilization over 4 weeks

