6.5.3.2 Follow up on potential drug-induced liver injury (DILI) cases

Patients with transaminase increase combined with total bilirubin (TBIL) increase may be indicative of potential DILI, and should be considered as clinically important events.

The threshold for potential DILI may depend on the patient's baseline AST/ALT and TBIL value; patients meeting any of the following criteria will require further follow-up as outlined below:

- For patients with normal baseline ALT and AST: AST or ALT $> 3.0 \times$ ULN combined with TBIL $> 2.0 \times$ ULN OR INR > 1.5 without evidence of cholestasis (no ALP elevation)
- For patients with elevated AST or ALT or TBIL value at baseline: [AST or ALT $> 2 \times$ baseline AND $> 3.0 \times$ ULN] OR [AST or ALT $> 8.0 \times$ ULN], combined with [TBIL $> 2 \times$ baseline AND $> 2.0 \times$ ULN]
- For patients with normal baseline ALT: ALT $\geq 5 \times$ Upper Limit of Normal (ULN)

Medical review needs to ensure that liver test elevations are not caused by cholestasis, defined as Alkaline Phosphatase (ALP) elevation $> 2.0 \times$ ULN with R value < 2 in patients without bone metastasis, or elevation of ALP liver fraction in patients with bone metastasis.

Note: (The R value is calculated by dividing the ALT by the ALP, using multiples of the ULN for both values. It denotes whether the relative pattern of ALT and/or ALP elevation is due to cholestatic (R ≤ 2), hepatocellular (R ≥ 5), or mixed (R > 2 and < 5) liver injury).

These patients should be immediately discontinued from eltrombopag, and repeat liver function test (LFT) testing as soon as possible, preferably within 48 hours from the awareness of the abnormal results, then with weekly monitoring of LFTs), or more frequently if clinically indicated, until AST, ALT, or bilirubin have resolved to baseline or stabilization over 4 weeks. The evaluation should include laboratory tests, detailed history, physical assessment and the possibility of liver metastasis or new liver lesions, obstructions/compressions, etc.

1. Laboratory tests should include ALT, AST, albumin, creatinine kinase, TBIL, direct and indirect bilirubin, gamma-glutamyl-transferase (GGT), prothrombin time (PT)/ International Normalized Ratio (INR) and ALP.

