10.2 Additional Safety Monitoring

10.2.1 Liver safety monitoring

To ensure patient safety and enhance reliability in determining the hepatotoxic potential of an investigational drug, a standardized process for identification, monitoring and evaluation of liver events has to be followed. Liver safety monitoring tests should be performed at local laboratories used by the site.

The following two categories of abnormalities / adverse events have to be considered during the course of the study (irrespective of whether classified/reported as AE/SAE):

- Significant liver laboratory abnormalities, which will require repeated assessments of the abnormal laboratory parameter
- Liver events, which will require close observation, follow-up monitoring and contributing factors are recorded on the appropriate CRFs

Please refer to [Table 6-4](#) for dose modifications/discontinuation for liver laboratory abnormalities.

Every clinically significant liver event should be followed up by the investigator or designated personnel at the trial site, as summarized below. Repeat liver chemistry tests (ALT, AST, TBL, PT/INR, ALP and GGT) to confirm elevation.

- These liver chemistry repeats should be performed locally. If a liver event is subsequently reported, any local liver chemistry tests previously conducted that are associated with this event should have results recorded on the appropriate (CRF). These liver chemistry repeats should be performed using the local laboratory used by the site. Repeated laboratory test results must be reported as appropriate.
- If the initial elevation is confirmed, close observation of the patient will be initiated, including consideration of treatment interruption if deemed appropriate.
- Discontinuation of the investigational drug (refer to the Discontinuation of study treatment section), if appropriate
- Hospitalization of the patient if appropriate
- Causality assessment of the liver event
- Thorough follow-up of the liver event should include
 - These investigations can include based on investigator's discretion: serology tests, imaging and pathology assessments, hepatologist's consultancy; obtaining more detailed history of symptoms and prior or concurrent diseases, history of concomitant drug use, exclusion of underlying liver disease

All follow-up information, and the procedures performed must be recorded as appropriate in the CRF.

[figure not shown]

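### For an isolated ALT rise from a normal baseline, Protocol 6.5.3.2 stops eltrombopag permanently from 5 x ULN, while Table 6-4 keeps the dose at exactly 5.0 and allows restart at >5–10 x ULN; nothing says which governs

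*Protocol*

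**What the plan says.** **Protocol 6.5.3.2 (follow-up of potential DILI).** Three criteria are given as alternatives, so meeting any one is enough. The third begins "For patients with normal baseline ALT: ALT" and sets the threshold at 5 x ULN or more, with no bilirubin or INR condition. The action follows the list: "These patients should be immediately discontinued from eltrombopag, and repeat liver function test (LFT) testing as soon as possible". No restart rule is given. The glossary describes study treatment discontinuation as "When the patient permanently stops taking study drug prior to the defined study treatment completion date" and treats interruption separately, as a temporary stop.

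**Protocol 6.5.2, Table 6-4, isolated AST or ALT elevation.** The row for >3.0–5.0 x ULN begins "Maintain dose level. Repeat LFTs". It calls for discontinuation only with symptoms of liver injury or decompensation, progressively rising tests, or persistence for 4 weeks or more. The row for >5.0–10.0 x ULN mandates interruption until the value resolves, and then: "If resolved in ≤ 14 days, maintain dose level If resolved > 14 days, decrease one dose level".

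**Text that might rank them.** Section 6.5.2 says: "Deviations to mandatory dose interruptions and/or reductions are not allowed". It also makes permanent discontinuation mandatory for the events that Table 6-4 marks as such. Section 10.2.1 refers the reader to Table 6-4 "for dose modifications/discontinuation for liver laboratory abnormalities". Section 6.5.2.1 lists ALT or AST above 20 x ULN among the reasons for permanent discontinuation. None of these mentions the 6.5.3.2 rule.

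**Elevated baseline.** Section 6.5.3.2 has a second criterion, "For patients with elevated AST or ALT or TBIL value at baseline". Table 6-4 has its own combined-elevation rule for elevated baseline AST or ALT, with a different transaminase trigger and the same bilirubin condition.

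**The concern.** Hepatotoxicity is an identified risk of the drug (Protocol 4.6), and two sections of one protocol attach different actions to the same laboratory value. A site cannot follow both once restart is in question.

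The conflict also reaches the primary endpoint. Under 6.5.3, a patient who permanently stops for a laboratory value leaves the study. Under 12.4.3, a patient who leaves before month 12 is not considered for sustained remission. Section 6.1.3 says instead that patients stopped for toxicity continue to be followed, but it denies them sustained remission as well. By either route the patient is a non-responder. An interrupted and restarted patient can still go on to taper and respond. Two sites could therefore classify the same laboratory course differently.

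The planned liver table in SAP 2.8.3 would not show which rule was followed. It pools ALT with AST, uses >5 rather than ≥5 x ULN and, as described, carries neither baseline status nor action taken.

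**Working it through.** **1. Normal baseline ALT, isolated rise, side by side.**

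| ALT (x ULN) | Protocol 6.5.3.2 | Table 6-4 |
|---|---|---|
| >3.0 to <5.0 | third criterion not met | maintain, with three exceptions |
| exactly 5.0 | discontinue | maintain, with three exceptions |
| >5.0 to 10.0 | discontinue | interrupt, then restart at the same or one lower dose level |

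The actions conflict from 5.0 to 10.0 x ULN inclusive. In the text available, the >5.0–10.0 cell holds two interruption instructions, and the rows there look shifted by extraction. Both instructions allow restart, so the conflict does not depend on this. No claim is made above 10 x ULN, where the rows cannot be read reliably.

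**2. Elevated baseline, combined with the bilirubin criterion.** Let B be baseline ALT or AST in multiples of ULN. Exclusion criteria 9 and 10 limit B to 3.0.

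- 6.5.3.2: (>2 x baseline and >3 x ULN) or >8 x ULN, so the trigger is min(max(2B, 3), 8).
- Table 6-4: the lower of 3 x baseline and 5 x ULN, so the trigger is min(3B, 5).

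| B | 6.5.3.2 | Table 6-4 |
|---|---|---|
| 1.2 | >3.0 | >3.6 |
| 1.5 | >3.0 | >4.5 |
| 1.67 | >3.33 | >5.0 |
| 2.0 | >4.0 | >5.0 |
| 2.5 | >5.0 | >5.0 |
| 3.0 | >6.0 | >5.0 |

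For 1.0 < B < 2.5, 6.5.3.2 is met first. The widest gap is at B = 5/3: 5.00 − 3.33 = 1.67 x ULN. For 2.5 < B ≤ 3.0, Table 6-4 is met first; the triggers differ there, but a site can comply with both.

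Example: baseline ALT 2.0, now 4.5, with bilirubin 2.5 x ULN from a normal baseline.

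- 6.5.3.2: 4.5 exceeds 2 x 2.0 = 4.0 and also 3.0, and the bilirubin condition is met, so the patient is discontinued.
- Table 6-4: 4.5 does not exceed min(6.0, 5.0) = 5.0, so the combined rule is not met and footnote c sends the site to the isolated-elevation rows. The bilirubin row interrupts with restart possible, or requires no dose change if the rise is indirect only. The ALT row maintains the dose.

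**3. Effect on the primary test.** Inputs are N = 105 and a cut-off of 23 (SAP 3.1.2), with P0 = 0.15. The p-value is the exact binomial upper tail, P(X ≥ k | 105, 0.15).

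- k = 23: 0.0373, which reproduces the SAP's 0.037.
- k = 22: 0.0626, above 0.05.
- One patient: 1/105 = 0.95 percentage points.

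**The case against.** The strongest reply is that the protocol points liver dosing decisions to Table 6-4. Sections 6.5.2 and 10.2.1 both send the reader there, and the isolated threshold in 6.5.2.1 is above 20 x ULN. Section 6.5.3.2 is headed as follow-up, opens with transaminase rises combined with bilirubin, asks for a review to exclude cholestasis, and says should where the table says mandatory. This makes Table 6-4 a reasonable guess at the intended rule, but it is not a statement of precedence. The third criterion stands alone, and excluding cholestasis leaves every non-cholestatic isolated rise in conflict. The conservative-action wording in footnote c covers combined elevations below the combined thresholds, not an isolated ALT rise.

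Four further points have force:

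- Above 5 x ULN both rules stop the drug at once, so immediate exposure is not in dispute. The case of exactly 5.0 is a single boundary value.
- The cut-off arithmetic would apply to any single reclassified patient. It does not show that this conflict touched one.
- Other planned outputs hold the pieces: dose changes with reasons and the dosing listing (SAP 2.4.1), laboratory listings (2.8.3), disposition reasons (2.3.1) and response-step flags (2.5.2). The gap is that none is described as bringing them together.
- According to SAP section 1, all 105 patients are enrolled and the primary CSR is final, so an amendment cannot change the month-12 classifications.

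These limit the likely size and the available remedy. They do not remove the contradiction.

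**Conclusion.** The concern holds. For a normal baseline ALT and an isolated rise, the protocol gives incompatible instructions from 5.0 to 10.0 x ULN and does not say which governs. The difference is maintain versus stop at exactly 5.0, and restart versus permanent stop above it. For an elevated baseline between 1.0 and 2.5 x ULN, the combined-elevation triggers differ by up to 1.67 x ULN, and the resulting actions can conflict.

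The number of affected patients is unknown. The effect on the primary result ranges from none (no affected patient, or a responder count away from the cut-off) to a changed decision (one patient at 23 versus 22). This rests on reading discontinued as the glossary defines it. If sites could read it as interrupted, the wording still needs one defined action.

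**What to change.** Reconcile Table 6-4 and section 6.5.3.2 so that each liver-test threshold carries one action: maintain, interrupt or permanently discontinue. State which passage governs, use one elevated-baseline trigger in both places, and align the cross-reference in 10.2.1. The thresholds and actions are for the sponsor's medical team to decide; this review takes no view on which are right. The cost is a clarification or amendment of two passages and one cross-reference, with no extra procedures.

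Where treatment is already complete, add one listing to the final CSR of every patient with ALT of 5 x ULN or more. It should show baseline ALT status, action taken (maintained, interrupted and restarted, or discontinued) and responder status. The laboratory values and dose changes are already collected (dose changes on the eCRF under Protocol 6.7), so this is a merge of existing data.

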6.6 Additional treatment guidance

6.6.1 Treatment compliance

The investigator must promote compliance by instructing the patient to take eltrombopag exactly as prescribed and by stating that compliance is necessary for the patient’s safety and the validity of the study. The patient must also be instructed to contact the investigator if he/she is unable for any reason to take eltrombopag as prescribed. Compliance will be assessed by the investigator and/or study personnel at each visit using pill counts (if applicable) and information provided by the patient. This information should be captured in the source document at each visit. All eltrombopag dispensed and returned must be recorded in the Drug Accountability Log.

6.7 Preparation and dispensation

The investigator or responsible site personnel must instruct the patient or caregiver to take the study drugs as per protocol. Eltrombopag will be dispensed to the patient by authorized site personnel only. All dosages prescribed to the patient and all dose changes during the study must be recorded on the Dosage Administration Record eCRF.

[figure not shown]
6.7.1 Handling of eltrombopag

Eltrombopag study treatment supplies must be received by a designated person at the study site, handled and stored safely and properly and kept in a secured location to which only the investigator and designated site personnel have access. Upon receipt, all study treatment must be stored according to the instructions specified on the labels and in the Investigator’s Brochure. Clinical supplies are to be dispensed only in accordance with the protocol. Technical complaints are to be reported to the respective Novartis CO Quality Assurance.

Medication labels will be in the local language and comply with the legal requirements of each country. They will include storage conditions for the study treatment but no information about the patient except for the medication number.

The investigator must maintain an accurate record of the shipment and dispensing of study treatment in a drug accountability log. Monitoring of drug accountability will be performed by monitors during site visits or remotely and at the completion of the trial. Patients will be asked to return all unused study treatment and packaging at the end of the study or at the time of discontinuation of study treatment.

At the conclusion of the study, and as appropriate during the course of the study, the investigator will return all unused study treatment, packaging, drug labels, and a copy of the completed drug accountability log to the Novartis monitor or to the Novartis address provided in the investigator folder at each site.

